9.5.2 Other Specifications

Summaries will be based on scheduled time points.
 In general, subject data listings should include all dosed subjects with data. However, if a subject data listing includes only subjects who met a certain condition, i.e., subjects with serious adverse events, and there are no subjects who met that condition, then a page marker will appear indicating that “No subjects met the condition for inclusion.”

9.6 Sample Size Calculation

Confidence Interval calculation has been performed for the primary performance endpoint “The proportion of subjects ('responders') with the lip volume improved by ≥ 1 point versus baseline value at 6 weeks after initial treatment based on the investigator live assessment using a validated Lip Fullness Scale (LFS)”. A responder is defined having at least ≥ 1 grade improvement compared to baseline values on the 5 point-validate lip fullness scale”.

Approximately 110 subjects with moderate to severe volume deficiency of lips will be enrolled in order to obtain performance and safety data.

This sample size is arbitrarily selected and is considered sufficient to provide robust estimations on performance and safety parameters in the overall study population and in the subgroups regarding IMD manufacturing site. With a sample size of 100, a two-sided 95% confidence interval for a single proportion using the large sample normal approximation will extend by 0.059 in the overall population and 0.083 in the two manufacturing site subgroups from the observed proportion for an expected proportion of 0.900 (i.e., responder rate of 90%; calculated with nQuery Advanced 8.2.1.0). In order to cover subjects’ drop-out or

lost to follow-up the sample size will be increased by 10%. 110 subjects will be enrolled (with 55 subjects per manufacturing site). Thus, a robust estimation of the success rate at week 6 can be derived.

9.7 Interim Analysis

An interim analysis (IA) assessing the safety and effectiveness will be performed after all subjects have completed the follow-up visit at Month 6 (Visit 4).

The interim analysis will be performed for the following endpoints using the “overall population”. Safety will be presented using SAF population and effectiveness will be estimated and presented for FAS population.

1. The proportion of subjects (‘responders’) with the lip volume improved by ≥ 1 point versus baseline value at 6 weeks after initial treatment based on the investigator live assessment using the validated Lip Fullness Scale (LFS).
2. The percentage of responders, based on the investigator live assessment at 6 months after the initial treatment using the validated LFS.
3. The percentage of subjects with an improvement relative to baseline photographs, (subjects who have been rated as “very much improved” or “much improved” or “improved”), based on the investigator assessment at Week 6, Month 6 after initial treatment using the 5-point GAIS.
4. The percentage of subjects with an improvement relative to baseline photographs (subjects who have been rated as “very much improved” or “much improved” or “improved”), based on subject assessment at Week 6, Month 6 after initial treatment, using the 5- point GAIS.
5. The extent of subject’s satisfaction with overall outcome of the treatment, at Week 6, Month 6 after initial treatment, assessed by the subject using the Face-Q™ Questionnaire “Satisfaction with Outcome”.
6. The extent of subject’s satisfaction with augmentation of lips, at Week 6, Month 6 after initial treatment, assessed by the subject using the Face-Q™ Questionnaire “Satisfaction with Lips”.
7. Subject’s perception of pain after initial and touch-up treatment with Saypha® FILLER Lidocaine using the 11-point Numeric Pain Rating Scale (NPRS), where 0 is no pain and 10 is the worst pain imaginable.
8. Percentage of subjects demonstrating an aesthetic effect at Week 6, Month 6 based on the investigator's life assessment.

9. Injection volume (initial and touch-up) required for an optimal augmentation of the lips with Saypha® FILLER Lidocaine.
10. Occurrence and frequency of adverse events
11. Baseline characteristics and demographics
12. Prior and concomitant medications and non-drug therapies
13. Subject disposition

9.8 Final Analysis

Final analysis will be done after completion of the investigation by all subjects. All primary, secondary and safety endpoints will be tabulated by visit, if applicable, and summarized using descriptive statistics only. The final analysis will be done for the 'overall population' and for several defined subgroups.

9.9 Statistical Software

All statistical analyses will be performed with SAS®, Version 9.4 or later.

10 Statistical Analyses

In this section detailed described about how each modules will be analyzed for interim analysis or for final analysis or for both.

10.1 Subject Disposition

Summary tables will be provided for the following subject characteristics:

- Number of subjects, both screened and received at least one administration of IMD, included in the study.
- Number of subjects by visit.
- Number of subjects included in the SAF, FAS and PPS.
- Number of subjects withdrawn from the study and the reason for withdrawal

Subjects who prematurely discontinue the study or lost to follow-up after receiving at least one dose of the IMD will be defined as dropouts.

10.2 Demographic Data and Baseline Characteristics

The demographic data and baseline characteristics will be analyzed using descriptive statistics in summary or frequency tables.

- Gender
- Age
- Race
- Smoking habits
- Lip Fullness Scale (LFS) - Investigator
- LFS - Independent photographic reviewer

10.3 Medical History and aesthetic procedures

All general medical / surgical history conditions will be coded using MedDRA version 23.0. General medical/surgical history conditions will be summarized by system organ class, preferred term and by Overall population using SAF population. The version of the utilized dictionary will be presented as part of the provided tables and listings. Listing of medical history will be provided.

10.4 Prior and concomitant medication

Prior and concomitant medications will be assessed at screening and at each subsequent study visit. Medications will be coded using WHODG B3 MAR 1, 2020.

Medication will be classified as prior, if the end date is known and is prior to the first use of the study IMD. Medications that are ongoing or ended after the first use of the study medication will be classified as concomitant. If the end date of the medication is unknown, it will also be considered as concomitant. Handling of missing date explained in section (Imputation of missing data section 9.5).

Prior and concomitant medications will be separately summarized by ATC class (the highest available level), preferred name for the safety population. Listings will be presented for prior and concomitant medications.

10.5 Treatment Exposure

The following will be assessed for initial and for touch-up treatment:

- number of subjects who received treatment,
- volume,
- technique and
- equipment used.

Descriptive statistics will be performed in total (i.e., both IMD administrations – initial plus touch-up treatment) and per single administration (initial and touch-up treatment, each) for the total volume (both lips) and volume per lip.

	Statistical Analysis Plan Sponsor: CROMA-PHARMA GmbH
	Study Number: CPH-101-201479 Version: Final 1.0 Date: 07 Jun 2021

Technique and equipment will be summarized by number and percentage using SAF population. Descriptive analysis will be performed for volume using SAF population.

Listings will be provided for initial and touch-up treatment

10.6 Effectiveness Endpoint

10.6.1 Primary Performance Endpoint

1. The proportion of subjects ('responders') with the lip volume improved by ≥ 1 point versus baseline value at 6 weeks after initial treatment based on the investigator live assessment using the validated Lip Fullness Scale (LFS).

'Responder' is defined having at least ≥ 1 grade improvement as evaluated with the 5-point validated LFS at a given visit relative to Baseline score (prior to treatment).. Individual LFS grades per visit will be calculated separately for the upper and the lower.

As two lips of each subject will be considered, there are two measurements per subject for LFS. Differences between the lips are expected, thus both measurements will be separately used for analyses.

Individual LFS grades per visit will be calculated separately to the upper and the lower lip, respectively. The absolute LFS change per lip versus baseline will be computed by subtracting the value obtained on Day 0 from that of the corresponding visit. Absolute LFS change from baseline will be summarized by the visit using descriptive statistics.

Subjects with the lip volume improved (≥ 1 point versus baseline) will be summarized by number and percentage using PPS and FAS population. Binomial proportion test at 5% level of significance will be performed to test the expected proportion of 0.900.

Listings will be provided for LFS.

	Statistical Analysis Plan Sponsor: CROMA-PHARMA GmbH
	Study Number: CPH-101-201479 Version: Final 1.0 Date: 07 Jun 2021

10.6.2 Secondary Performance Endpoint

1. The percentage of responders, based on the investigator live assessment at 6, 12 and optional 18 months after the initial treatment using the validated LFS.

Percentage of responders, based on the investigator live assessment at 6, 12 and optional 18 months after the initial treatment using the validated LFS will be summarized by number and percentage using PPS and FAS population.

2. The percentage of responders based on the independent photographic reviewer’s assessments before initial treatment and at Week 6, Month 6, 12 and optional Month 18 after initial treatment, based on photographs and using the validated LFS.

Percentage of responders based on the independent photographic reviewer’s assessments before initial treatment and at Week 6, Month 6, 12 and optional Month 18 after initial treatment, based on photographs and using the validated LFS will be summarized by number and percentage using PPS and FAS population.

3. The percentage of subjects with an improvement relative to baseline photographs, (subjects who have been rated as “very much improved” or “much improved” or “improved”), based on the investigator assessment at Week 6, Month 6, 12 and optional Month 18 after initial treatment using the 5-point GAIS.

Percentage of subjects with an improvement relative to baseline photographs (subjects who have been rated as “very much improved” or “much improved” or “improved”), based on investigator assessment at Week 6, Month 6, 12 and optional Month 18 will be summarized by number and percentage using PPS and FAS population.

Listings will be provided for GAIS.

4. The percentage of subjects with an improvement relative to baseline photographs (subjects who have been rated as “very much improved” or “much improved” or “improved”), based on subject assessment at Week 6, Month 6, 12 and optional Month 18 after initial treatment, using the 5-point GAIS.

Percentage of subjects with an improvement relative to baseline photographs (subjects who have been rated as “very much improved” or “much improved” or “improved”), based on subject assessment at Week 6, Month 6, 12 and optional Month 18 will be summarized by number and percentage using PP and FAS population.

5. The extent of subject’s satisfaction with overall outcome of the treatment, at Week 6, Month 6, 12 and optional Month 18 after initial treatment, assessed by the subject using the Face-Q™ Questionnaire “Satisfaction with Outcome”.

The extent of subject's satisfaction with overall outcome of the treatment, at Week 6, Month 6, 12 and optional Month 18 after initial treatment, assessed by the subject using the Face-Q™ Questionnaire "Satisfaction with Outcome" for each question will be summarized by number and percentage using PPS and FAS population.

Face Q data will be analyzed according to the FaceQ USER'S GUIDE (VERSION 1.0 January 2015). The raw summed scale score is converted to a score from 0 to 100 by using the respective Conversion Tables available from the authors. Higher scores reflect a better outcome (i.e., 0 (worst) to 100 (best)).

Listings will be provided for Face-Q™ Questionnaire "Satisfaction with Outcome".

6. The extent of subject's satisfaction with augmentation of lips, at Week 6, Month 6, 12 and optional Month 18 after initial treatment, assessed by the subject using the Face-Q™ Questionnaire "Satisfaction with Lips".

The extent of subject's satisfaction with augmentation of lips, at Week 6, Month 6, 12 and optional Month 18 after initial treatment, assessed by the subject using the Face-Q™ Questionnaire "Satisfaction with Lips" for each question will be summarized by number and percentage using PPS and FAS population.

Listings will be provided for Face-Q™ Questionnaire "Satisfaction with Lips".

7. Subject's perception of pain after initial and touch-up treatment with Saypha® FILLER Lidocaine using the 11-point Numeric Pain Rating Scale (NPRS), where 0 is no pain and 10 is the worst pain imaginable.

Subject's perception of pain after initial and touch-up treatment with Saypha® FILLER Lidocaine using the 11-point Numeric Pain Rating Scale (NPRS) will be analyzed descriptively using PPS and FAS populations.

Paired t-test will be performed to check the mean difference between "immediately after" and "15 minutes later at each visit are significant at 5% level of significance.

Listings will be provided for Numeric Pain Rating Scale (NPRS).

8. Percentage of subjects demonstrating an aesthetic effect at Week 6, Month 6, 12 and optional Month 18 based on the investigator's life assessment.

Percentage of subjects demonstrating an aesthetic effect at Week 6, Month 6, 12 and optional Month 18 based on the investigator's life assessment will be summarized by number and percentage using PPS and FAS population.

	Statistical Analysis Plan Sponsor: CROMA-PHARMA GmbH
	Study Number: CPH-101-201479 Version: Final 1.0 Date: 07 Jun 2021

9. Injection volume (initial and touch-up) required for an optimal augmentation of the lips with Saypha® FILLER Lidocaine

Summary of injection volume (initial and touch-up) required for an optimal augmentation of the lips by upper and lower lips will be analyzed descriptively using FAS and Safety analysis set for Overall population.

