	Screening/ Baseline	Telephone Visit	Touch up	Telephone Visit		Month 6	Month 12	Optional ^{††} Month 18
Assessment	Day 0*	24h after	Week 3	24h after	Week 6	Week 26	Week 52	Week 76
		IMD admin.)	± 2 days	IMD admin.)	± 5 days	± 7 days	± 7 days	± 7 days
	Visit 1	Visit 1a	Visit 2	Visit 2a	Visit 3	Visit 4	Visit 5	Visit 6
Informed consent	X**							
Eligibility assessment	X**							
Urine pregnancy test ^b	X**				Х	х	Х	х
Demographic data ^a	X**							
Medical history	X**							
Photography	X**				Х	Х	Х	Х
Initial treatment	х							
Touch-up treatment			(x) [†]					
LFS - independent photographic reviewer	х				Х	х	Х	х
LFS - investigator ^c	X**				Х	Х	Х	Х
GAIS - investigator					Х	х	Х	х
GAIS - subject					Х	Х	Х	Х
FACE-Q [™] "Satisfaction with outcome" - subject					Х	Х	Х	Х
FACE-Q [™] "Satisfaction with lips" - subject					Х	Х	Х	Х
Assessment of aesthetic effect - investigator					Х	Х	Х	Х
Pain assessment ^e using the NPRS - subject	х		(x) [†]					
Prior and concomitant medication	X**	х	х	х	Х	х	х	х
Adverse event ^d	X***	x§	X***	x§	Х	х	х	х
Device deficiencies	Х		(x) [†]					

CONFIDENTIAL

- Includes screening and (initial) treatment
- ** Prior to application of the investigational device
- *** In order to identify potential AEs post-administration of IMD, AEs should be assessed 15 minutes after each administration (initial and touch-up treatment).
- [†] Touch-up treatment is optional (at investigator's discretion, if full correction was not achieved after initial treatment).
- The duration of the clinical investigation is planned for 18 months at a maximum and depends on the assessment of the aesthetic effect. In case it is observed by the investigator that no aesthetic effect is any more visible the study can be terminated at Month 12 (Visit 5) for the respective subject.
- Safety follow-up via telephone: Any adverse events since injection? In case of an AE an unscheduled on-site visit should be performed.
- a Includes year of birth, sex, race, and smoking status
- In females of child-bearing potential only, including women who are postmenopausal for less than 12 months
- ^c Evaluated by the investigator using LFS. The upper and lower lip will be graded separately
- To be collected throughout the investigation, beginning immediately after start of initial treatment until the last visit.
- e NPRS: Immediately and 15 minutes after initial and touch-up IMD treatment.

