6.1 Design description

This is a prospective, open-label, multicentre, randomized investigation to evaluate the effectiveness, safety and long-term safety of Saypha® FILLER Lidocaine for bilateral lip augmentation and to assess the duration of the aesthetic effect of the device. As justified in section 3.3, this type of design is considered appropriate in view of the purpose and objectives of the study.

The investigation comprises of six on-site visits within 18 months (76 weeks):the Screening/Baseline visit (Visit 1/Day 0) and 5 follow-up visits at 3 weeks (Visit 2), 6 weeks (Visit 3), 6, 12, and 18 months after initial treatment (Visits 4, 5 and 6). Visit 6 at Month 18 is an optional visit. In case it is observed by the investigator at the 12 months visit (Visit 5) that no aesthetic effect is any more visible the study can be terminated at Visit 5. Subjects will randomly be assigned to one of the two IMDs at a 1:1 ratio ('IMD-HQ': 'IMD-C1').

The Screening/Baseline visit (Visit 1) will entail informed consent and screening assessments as specified in section 6.5.1. During this visit the investigator will determine the inclusion of subjects based on inclusion/exclusion criteria (see sections 6.3.3 and 6.3.4).

Eligible subjects will be randomized to one of the IMDs ('IMD-HQ' or 'IMD-C1') and undergo bilateral lip augmentation treatment with Saypha® FILLER Lidocaine in order to correct moderate to severe deficiency of lip volume at Visit 1 (Day 0). In addition to this initial treatment an optional touch-up treatment can be performed at Visit 2 (Week 3) in order to achieve optimal cosmetic corrections (in the discretion of the investigator). The injection volume will be recorded at each treatment visit (i.e., Visit 1 and Visit 2) (see section 6.4.6). 24 hours after each treatment a telephone visit will be performed for safety evaluation (Visit 1a and Visit 2a in case of touch-up treatment; see sections 6.5.2 and 6.5.4).

Baseline severity of lip volume deficiency will be determined at Visit 1 by the investigator using a validated 5-point Lip Fullness Scale (LFS) before the initial treatment. The LFS will be repeated 6 weeks and 6, 12 and optional 18 months after the initial IMD treatment. Independent photographic reviews will be performed at the same time points using LFS on photographs (see section 6.4.7).

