6.3.5 Withdrawal criteria and procedures

The subject may be withdrawn from the investigation for any of the following reasons:

- 1. Occurrence of an AE which requires a premature termination of the treatment or precludes followup of the subject
- 2. A major CIP deviation, which may interfere with evaluation of the treatment outcome (e.g., additional aesthetic correction of the defect during the course of the study, use of prohibited medication, or similar)
- 3. Investigator's decision, triggered by safety, behavioural or administrative reasons
- 4. Pregnancy
- 5. Informed consent withdrawal

A subject is free to withdraw the consent and leave the investigation at any time with no obligation to specify the reason for withdrawal.

Efforts should be made, however, to get in touch with subjects who did not attend the scheduled visit and clarify the reason for default. If the subject is unreachable, a corresponding note should be provided in the subject's medical record.

Reasons, circumstances and findings related to early withdrawal should be fully described in the subject's medical records and the eCRF respecting the subject's rights.

Attempts should be made to perform an early termination visit, which should consist of the assessments planned for the Month 18 visit (Visit 6; also see section 6.5.6). In the event that the withdrawal is caused by an AE, the procedures stated in section 14.6 must be followed.

Depending on the time point of withdrawal, a withdrawn subject is referred to as either "screening/baseline failure" or "dropout" as specified in section 6.3.10.

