6.4.8 Numeric Pain Rating Scale (NPRS) - Pain assessment

After initial administration and touch-up treatment of the IMD, the subject will be asked by the investigator to quantify the pain associated with the procedure by means of a semi-quantitative 11-point Numeric Pain Rating Scale (NPRS), where 0 corresponds to no pain, and 10 to the worst pain imaginable.¹⁷

Pain intensity will be assessed twice, immediately after injection, and approximately 15 minutes thereafter, by asking the subject one of the following questions, as appropriate:

- "How would you rate the pain you have felt during the treatment, if "0" is no pain at all, and "10" is the worst pain you can imagine?"
- "How would you rate the pain you have felt during recovery from the treatment, if "0" is no pain at all, and "10" is the worst pain you can imagine?"

Subject's response will be recorded on the Pain Assessment Form. The subject will be provided with the appropriate questionnaire in local language.

Completed subject's Pain Assessment Form will be considered as source documents and archived in the subject's medical record. The results will be transferred into the eCRF.

To avoid over-reporting of pain, a non-leading question "How do you feel?" should be asked prior to pain assessment. Only spontaneously reported pain, or pain graded ≥4 will be recorded as an AE according to the procedures described in section 14.

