9.2 Analysis Population

Analysis Population	Definition
Safety Analysis Set (SAF)	The Safety Analysis Set (SAF) consists of all subjects who received at least one administration of the investigational medical device (IMD).
Full Analysis Set (FAS)	The Full Analysis Set (FAS) comprises all subjects who received at least one administration of the IMD and who had at least one post-treatment evaluation of the LFS.
Per-Protocol Set (PPS)	The Per-Protocol Set (PPS) includes all subjects of the FAS who have no major protocol deviations which affect the primary endpoint. Subjects with major protocol deviations which affect the primary endpoint will be excluded from the PPS.

	Statistical Analysis Plan	
	Sponsor: CROMA-PHARMA GmbH	
	Study Number: CPH-101-201479	Version: Final 1.0 Date: 07 Jun 2021

For this purpose, protocol deviations that could interfere with the objectives of the study, use of prohibited concomitant medications/procedures or deviation of the inclusion/exclusion criteria etc. will be assessed as ‘minor’ or ‘major’ in collaboration with the sponsor in the Data Review Meeting (DRM). The criteria for this assessment will be defined before analysis in the SAP. Listings will be prepared to assess the eligibility of all subjects during the DRM.

All safety analyses will be based on the SAF. The primary data set for effectiveness analysis will be the FAS and PPS.

Subjects who have been administered wrong IMD which is different from randomized will be analyzed as randomized (Planned) for FAS and will be analyzed under IMD, which was administered at first, for SAF. These subjects will not be included in PPS.

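### Pain (NPRS) is summarised only in the FAS and PPS, so treated subjects with no post-treatment LFS at all are left out although their pain ratings are valid

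*SAP*

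**What the plan says.** **Timing of the rating.** Protocol 6.4.8: "Pain intensity will be assessed twice, immediately after injection, and approximately 15 minutes thereafter". The footnote to Table 1 of the protocol agrees: "NPRS: Immediately and 15 minutes after initial and touch-up IMD treatment". The ratings therefore fall on Day 0 and, for subjects who have a touch-up, at Week 3.

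**Analysis sets.** SAP 10.6.2 item 7: the "Numeric Pain Rating Scale (NPRS) will be analyzed descriptively using PPS and FAS populations". The same item plans a paired t-test of the two ratings at each treatment visit. SAP 9.7 presents effectiveness at the interim in the FAS. SAP 10.8 lists NPRS among the endpoints analysed by IMD, technique and equipment, in the FAS only.

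**Who is in each set.** The SAF is every subject treated at least once. The FAS adds the condition that it contains those "who had at least one post-treatment evaluation of the LFS" (SAP 9.2). The PPS removes from the FAS subjects with major deviations that affect the primary endpoint.

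**When the LFS is taken.** Protocol 6.1: "The LFS will be repeated 6 weeks and 6, 12 and optional 18 months after the initial IMD treatment". For withdrawn subjects, protocol 6.3.5 adds: "Attempts should be made to perform an early termination visit, which should consist of the assessments planned for the Month 18 visit". Protocol 6.5.6 puts the investigator LFS among the minimum assessments recommended at that visit.

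**A comparable endpoint.** Injection volume (SAP 10.6.2 item 9), also recorded on the treatment day, "will be analyzed descriptively using FAS and Safety analysis set for Overall population".

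**The concern.** Whether a pain rating is counted depends on something that happens after it was given and that has nothing to do with pain. A subject can complete both Day 0 ratings, or four ratings if there is a touch-up, and still be absent from every NPRS table because no LFS followed. If such subjects found the injection more painful than the rest, mean NPRS would be understated.

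The SAP is also uneven on this point. Injection volume and treatment exposure (SAP 10.5) are summarised in the SAF, as are adverse events. A rating of 4 or more can therefore count as an adverse event in the SAF while the rating itself is missing from the NPRS table.

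Reduction of procedural pain is the stated purpose of the lidocaine (protocol 2.1, Table 3). Protocol 6.3.8 bars anaesthetic pre-treatment to protect the pain assessment. Valid ratings should not be set aside without a reason.

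**Working it through.** **Step 1. Follow treated subjects through the definitions.** All have Day 0 ratings.

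| Course after treatment | SAF | FAS | In the NPRS summary (FAS) |
|---|---|---|---|
| Lost before Week 6, no further visit | yes | no | no |
| Touch-up at Week 3, then lost, no further visit | yes | no | no (four ratings) |
| Leaves before Week 6, early termination visit with LFS | yes | yes | yes |
| Misses Week 6, has LFS at Month 6 | yes | yes | yes |

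The Week 3 visit has no LFS (Table 1; protocol 6.5.3), so attending it does not bring a subject into the FAS. Only subjects with no LFS at all after treatment are left out.

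**Step 2. The plan's own loss figure.** SAP 9.6 and protocol 7.1 start from 100 subjects and add 10%: 100 × 1.10 = 110. This reproduces the stated enrolment and allows for 10 losses. The allowance is not split by time, and no rate of loss before Week 6 is given.

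**Step 3. Formula.** Let N be the number treated, m the number of these outside the FAS, F the mean NPRS in the FAS, and F + d the mean among the m. Then

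SAF mean = [(N − m) × F + m × (F + d)] / N = F + (m/N) × d,

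so the FAS mean is lower than the SAF mean by (m/N) × d.

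**Step 4. Numbers.** N = 110 assumes that all enrolled subjects are treated. Both m and d are assumptions, because the documents give neither.

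| m | d (points) | Calculation | FAS mean lower by |
|---|---|---|---|
| 0 | any | 0/110 × d | 0 |
| 3 | 2 | 3/110 × 2 | 0.05 |
| 10 | 2 | 10/110 × 2 | 0.18 |
| 10 | 4 | 10/110 × 4 | 0.36 |

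The rows with m = 10 place the whole allowance before any LFS. They are an upper case, not an expectation.

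**Step 5. One IMD arm.** With 55 subjects per arm, three losses all in one arm and a 2-point gap shift that arm by 3/55 × 2 = 0.11 points.

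**Step 6. Scale.** For an assumed NPRS standard deviation of 1.5 to 2.5, the 95% half-width of a mean in 110 subjects is 1.96 × 1.5/√110 = 0.28 to 1.96 × 2.5/√110 = 0.47. The shift with three losses is well inside that range; the upper case is of similar size.

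**The case against.** A reader might infer that the FAS requires an LFS at Week 6 or later, and so that everyone who leaves early, including because of pain or an adverse event, drops out of the pain result. The documents do not support that. The FAS definition names no visit. Withdrawn subjects are to be offered an early termination visit with the Month 18 assessments, and the investigator LFS is on its recommended minimum list. An adverse event reported by telephone should lead to an on-site visit (protocol 6.5.2 and 6.5.4), and if an unscheduled visit ends participation, the early termination assessments follow (6.5.7). Subjects who leave because of an adverse event thus have a route into the FAS. This stands and narrows the point. It does not remove it: the visit is only to be attempted, its content is only recommended, and it cannot reach subjects who are lost or who refuse to return.

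It can also be said that pain is already covered in the SAF. Protocol 3.3 makes adverse events the main source on the occurrence of pain, with NPRS as added information on intensity. Pain that is spontaneously reported or rated 4 or more is recorded as an adverse event (6.4.8), and adverse events are analysed in the SAF (SAP 10.7.1). NPRS is listed, and listings generally cover all dosed subjects with data (SAP 9.5.2). This stands too: the information is not lost. But adverse event tables do not give mean NPRS and do not show low ratings that were not volunteered, and a listing is not an estimate.

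Finally, NPRS is a performance endpoint, and the protocol synopsis assigns effectiveness analyses to the FAS and PPS. That is a sound reason not to replace those sets. It is no obstacle to adding one, as item 9 shows.

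**Conclusion.** The point holds in a narrow form. Treated subjects with no LFS after treatment are omitted from the NPRS summary, the paired t-test and the NPRS subgroup tables, although their ratings were complete before they left. The shift in mean NPRS is 0 if there are no such subjects, 0.05 points in a modest case and 0.18 to 0.36 points in an upper case. It is probably small. These sizes rest on assumed numbers lost and assumed gaps in pain.

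A reader might also infer that the reported pain is biased downwards. That is plausible but not shown: the documents say nothing about pain in early leavers, and the withdrawal reasons in protocol 6.3.5 also include pregnancy, administrative decisions and withdrawn consent. The case for a change is that the data exist, the selection is avoidable and the cost is low.

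**What to change.** In SAP 10.6.2 item 7, add the SAF (all treated subjects with a rating) as an analysis set for NPRS, including the paired t-test. Do the same for NPRS in SAP 9.7, for the overall population only, since the interim is confined to it, and in SAP 10.8 by IMD, technique and equipment. Keep the FAS and PPS where they are now specified, as the CIP requires.

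Record the addition in SAP section 11 and check it against protocol 7.7, which calls for a CIP amendment where a deviation affects the effectiveness analysis. In the by-IMD table, note that SAP 9.2 groups the SAF by the IMD first given and the FAS by the IMD assigned, so the two tables could also differ for that reason.

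The cost is one extra set of tables and a documented change from the CIP. No new data are needed.
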